## 4. Study population

### 4.1 Inclusion criteria

1. The age is between 18 and 80 years old.
2. Stage T1a or T1b according to the 8th edition of the AJCC TNM staging of kidney cancer, 2017.
3. The patients who underwent PN or TE between 2014 and 2022.

### 4.2 Exclusion criteria

1. With severe active infection or serious cardiac, hepatic, renal and hematopoietic diseases; and other physical conditions that make them unsuitable for the test in question (as judged by the investigator).
2. The patient has no measurable or evaluable lesions.
3. The tumor is close to the collecting system, touching the renal artery or renal vein, and other anatomical conditions that are not

suitable for nephrectomy.

4. History of organ transplantation or need for long-term adrenocorticotrophic hormone therapy; hypothyroidism, adrenal or pituitary function that cannot be controlled with hormone replacement therapy alone, type I diabetes, psoriasis or vitiligo requiring systemic treatment, etc.

5. The presence of active infection requiring systemic therapy. The presence of human immunodeficiency virus (HIV) infection (known to be HIV antibody positive). The presence of active HBV or HCV infection (HBsAg positive individuals, or HBcAb positive but HBsAg negative individuals who require additional DNA quantification and whose results do not exceed the upper limit of normal values in the study center laboratory can participate in this study. Previous HCV infected patients with negative HCV RNA test results during the screening period can participate in this study).

6. Have a history of kidney surgery or any inflammatory kidney surgery, have kidney cancer associated with the urinary collection system, and have other kidney diseases (including kidney stones and glomerulonephritis).

## **5. Experimental program**

**5.1** The patients are screened according to the inclusion and exclusion criteria. Then the patients are divided into two groups according to whether they underwent zero-ischemic enucleation or partial nephrectomy, with the zero-ischemic enucleation group as the test group and the partial nephrectomy group as the control group. Describing the preoperative conditions (age, sex, Anatomy of tumor, RENAL score, ABC score, preoperative renal function), the perioperative conditions (operation time, intraoperative bleeding, perioperative complications, negative/positive specimen margins, postoperative renal function changes, postoperative hospitalization days), and the postoperative condition (follow-up renal function, tumor recurrence rate, overall survival, tumor-free survival, progression-free survival).

**5.2** The data of the two groups are corrected for baseline and screened so that there is no statistical difference in the number of patients, gender age, tumor anatomy, renal function and other preoperative conditions between the two groups (t-test/rank sum test  $p > 0.05$ ).

**5.3** The zero ischemic renal enucleation group is grouped according to RENAL score, ABC score and other scoring criteria. Different preoperative tumor score groupings are used as exposure

factors, and the percentage decrease of postoperative renal function compared with preoperative, perioperative complication rate and postoperative survival rate are used as outcome variables to analyze the association between exposure factors and outcome, to investigate the association of different factors on the surgical outcome of zero ischemic renal enucleation.

**5.4** Using zero-ischemic nephrectomy or partial nephrectomy with clamping of the renal hilum as the exposure factor. T-test/rank sum test and one-way regression are used to compare the efficacy indexes such as negative/positive tumor margins, postoperative and follow-up renal function, survival rate, and safety indexes such as perioperative complication rate and intraoperative bleeding between the two groups to investigate whether there is a statistical difference in their treatment safety and efficacy. Then we investigated whether there are statistical differences and correlations between the safety and efficacy of the treatment, and whether there are statistical differences in survival outcomes between the two groups by multifactorial cox regression.

[figure not shown]

Figure 2. Experimental flow

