**DATE: February 10, 2023**

# 1. Research Background

Renal cell carcinoma(RCC) is a common tumor of the urinary system, accounting for 4.1% of all malignant tumors. 1 According to the latest GLOBOCAN data, in 2021, there are 71,676 new cases and 15,259 deaths of kidney cancer in the United States and 77,410 new cases and 46,345 deaths in China. The incidence of kidney cancer in China has increased at an average annual rate of 6.5% over the past 20 years and has surpassed bladder cancer in the number of deaths related to urological tumors, ranking first. Since renal ultrasound is a routine medical examination for people over 40 years old in China, most of the patients are in the early stage of limited renal cancer when they are diagnosed.

In the current guidelines, nephron sparing surgery(NSS) is the preferred treatment for early-stage limited kidney cancer. NSS includes partial nephrectomy(PN) and tumor enucleation(TE). Unlike PN, TE is a surgical procedure that bluntly separates the tumor along the natural cutting plane between the pseudocapsule and healthy parenchyma, completely removing the tumor tissue while maximizing the preservation of normal kidney tissue. However, most surgeons currently perform partial nephrectomy. The reason for this phenomenon is first, the problem of concept. most surgeons doubt whether TE can clean up tumor tissue. on the other hand, enucleation requires surgeons to have a better understanding of the anatomical relationship around the tumor and accurately separate the tumor envelope and normal kidney tissue, and its surgical difficulty is higher than that of traditional PN.

Our team has conducted a clinical meta-analysis on these two procedures, and the results showed that TE has the advantages of less trauma, faster postoperative recovery, and better protection of renal function than PN, without increasing the risk of tumor recurrence.

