Minervini et al. analyzed the pseudocapsule integrity of 304 specimens after TE, founding that 51% of the specimens had an intact pseudocapsule and 49% had infiltrating tumor cells on the pseudocapsule. but all specimens had negative cut margins and there is no statistical difference in 5-year progression-free survival. thus they concluded that enucleation for renal cancer is a safe surgical procedure. In the past 10 years, our team has performed more than 500 kidney cancer enucleations without any positive margins and no patient has experienced in local recurrence. In addition, traditional PN requires temporary blockage of the renal artery to achieve a relatively bloodless operating environment to ensure the safety of tumor removal. But prolonged warm ischemia is bound to affect the function of normal kidney tissue. Therefore reducing thermal ischemia time up to zero ischemia time has become a quest for surgeons. The combination of zero-ischemia technique on the basis of kidney cancer enucleation is a field that has rarely been touched.

Therefore reducing thermal ischemia time up to zero ischemia time has become a quest for surgeons. Clinically, the combination of zero-ischemia technique on the basis of kidney cancer enucleation is a field that has rarely been touched. In the last 3 years, our team has performed nearly 100 cases of zero-ischemic renal tumor enucleation, and this procedure can maximize the protection of renal parenchyma and renal function under the premise of ensuring tumor safety. In conclusion, if zero ischemia enucleation can be applied and popularized to limited renal cancer surgery, it will benefit a large number of patients and improve the prognosis.

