## **3. Study content and design**

This study aims to evaluate the effectiveness and safety of the surgery by using renal cancer patients who met the inclusion criteria. Summarizing the preoperative, perioperative, and postoperative data, and evaluating the operative time, intraoperative bleeding, postoperative hospitalization days, postoperative complication rate, postoperative short-term, intermediate, and long-term renal function indexes, overall survival, tumor-free survival, progression-free survival and postoperative renal cancer recurrence rate of the patients.

Statistical software is used to describe the characteristics of patient data. T-test, rank sum test, multi-factor regression, and cox regression are used to investigate the effects of each factor on the treatment outcome and prognosis of patients undergoing zero-ischemic renal enucleation, to describe whether there are differences in the safety and efficacy of zero ischemic renal enucleation compared with traditional

partial nephrectomy for the treatment of stage T1 renal carcinoma.

This study used a retrospective research trial design to include 73 patients who underwent zero-ischemic enucleation and 73 patients who underwent traditional partial nephrectomy from 2014 to 2022, for a total of 146 patients. The formula for calculating the sample size is as follows.

$$n = [z_{\alpha}\sqrt{2\bar{p}\bar{q}} + z_{\beta}\sqrt{p_0q_0 + p_1q_1}]^2 p / (p_1 - p_0)^2$$

Figure 1. Estimated sample size calculation

note:  $Z_{\alpha}$ 、 $Z_{\beta}$  are the quartiles under standard normal distribution.

$p_1$ : Expected morbidity in the exposed group.

$p_0$ : Expected incidence in the control group.

$q_1$ :  $q_1 = 1 - p_1$ .

$q_0$ :  $q_0 = 1 - p_0$ .

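### Patients are grouped by the operation they ended up having, so an off-clamp enucleation that is later clamped has no group, and one finished as a clamped resection meets the control definition

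*Combined protocol and SAP*

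**What the plan says.** Three places decide who is in the study and in which group, and all three refer to the operation the patient had:

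- Section 3 counts "73 patients who underwent zero-ischemic enucleation and 73 patients who underwent traditional partial nephrectomy from 2014 to 2022".
- Section 4.1, item 3, admits "The patients who underwent PN or TE between 2014 and 2022".
- Section 5.1 states that "the patients are divided into two groups according to whether they underwent zero-ischemic enucleation or partial nephrectomy", with enucleation as test and partial nephrectomy (PN) as control.

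Section 5.4 is narrower about the control, naming "partial nephrectomy with clamping of the renal hilum as the exposure factor". The secondary objectives in Section 2 also specify PN with the hilum clamped. Section 1 treats PN and tumour enucleation (TE) as two distinct operations.

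Section 5.1 lists as data to describe "the perioperative conditions (operation time, intraoperative bleeding, perioperative complications, negative/positive specimen margins, postoperative renal function changes, postoperative hospitalization days". Technique attempted, clamp time and conversion are not in that list. Section 5.2 screens the groups for balance on preoperative characteristics. No readable section mentions planned approach, unplanned clamping or conversion. Figure 2, the study flow, is not shown, so a rule there cannot be excluded.

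**The concern.** A surgeon can plan an enucleation without clamping but knows only during the operation whether it stayed unclamped. Grouping by what was completed lets an intraoperative event decide membership of the test group. Section 1 itself ties clamping to two of the study's outcomes: it describes clamping as the means of getting a nearly bloodless field, and prolonged warm ischaemia as harmful to the kidney. Bleeding, complications and change in GFR are all outcomes in Section 2.

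If attempts that went badly leave the test group, its remaining results look better than those of everyone in whom the technique was tried. That is a systematic error, so neither the p-value nor the confidence interval shows it. A surgeon choosing a technique chooses what to attempt, and needs the result for all attempts.

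**Working it through.** **Where each kind of case falls, on the wording as it stands**

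| Course of the operation | Section 4.1 item 3 | Group under 5.1 and 5.4 |
|---|---|---|
| Enucleation, never clamped | eligible (TE) | test |
| Enucleation begun off-clamp, then clamped | eligible (TE) | neither: not zero-ischaemia, not PN |
| Enucleation begun off-clamp, finished as clamped resection | eligible (PN) | meets the control definition |
| PN with clamping, completed | eligible (PN) | control |
| PN converted to nephrectomy | not a completed PN | neither |

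Clamping status must already be known to form the groups. What the listed data do not separate is planned from unplanned clamping.

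**Inputs for the size**

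- From the document: 73 per group (Section 3). The sample size formula there has no values for its expected proportions in the readable text, so 73 cannot be reproduced; it is taken as given.
- Assumed, because the documents give no figure: conversion rate in the test group c = 0 to 15%; excess complication risk of converted over completed cases e = 15 to 30 points; complication risk for the standard error 10%.

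**Shift from dropping converted attempts**

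If completed cases have risk r and converted cases r + e, the risk over all attempts is (1 − c)r + c(r + e) = r + c·e. Completed cases alone give r. The shift is therefore c·e:

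- Lowest: 0 × 15 = 0 points.
- c = 3%, e = 30: 0.03 × 30 = 0.9 points.
- Highest: 0.15 × 30 = 4.5 points.

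**Comparison with sampling error**

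SE of the difference = √(2 × 0.10 × 0.90 / 73) = 0.0497, or about 5.0 points. The largest shift is 4.5 / 4.97 = 0.91 standard errors.

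**Direction**

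PNs converted to nephrectomy also drop out. With a PN conversion rate d = 0 to 5% and the same range of excess risk (both assumed), the net shift is c·e in the test group minus d·e in the control group. It runs from 0 − 0.05 × 30 = −1.5 points to 4.5 − 0 = 4.5 points. For example, c = d = 5% with an excess of 15 points in the test group and 30 in the control group gives 0.75 − 1.5 = −0.75. The sign is probable, not fixed.

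**The case against.** The best reply is that this is a choice of question. In a retrospective study, the effect of a completed zero-ischaemia enucleation is a coherent target, and cases that fit neither group are in effect excluded. Section 4.2, item 3, already removes difficult anatomy and so may make conversions rare. Every rate above is assumed, the range includes zero, and the dropped-case shift stays below one standard error.

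Much of that stands. It limits the size of the point but does not remove it. The plan does not say that it targets completed operations only, does not count what that excludes, and on its wording could place a failed attempt in the control group.

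Three stronger readings are tempting and are not supported:

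- *Conversions must have occurred.* Section 1 says that over ten years "our team has performed more than 500 kidney cancer enucleations" and that in the last three "our team has performed nearly 100 cases of zero-ischemic renal tumor enucleation". A reader might infer that the remainder include failed off-clamp attempts. The figures concern clamped or unspecified enucleations, not converted ones. The others may have been planned with clamping, and such cases properly lie outside this comparison.
- *The bias is much larger because converted cases inflate the control rate.* That needs a high conversion rate, a large excess risk, many conversions recorded as PN, and those cases landing among the 73 selected controls. The documents support none of these, and a larger PN pool would dilute them.
- *The control group is contradictory.* Sections 4.1 and 5.1 say PN without qualification, but Section 1 describes traditional PN as requiring temporary arterial occlusion, and Section 3 names the controls as traditional PN. Read together with Sections 2 and 5.4, the control is largely identified as clamped PN; the looser wording needs clarifying.

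**Conclusion.** The concern holds as a gap in the classification rule, and the change is worth making. On the readable text, the rule can sort patients by an intraoperative event related to the outcomes, and nothing in Section 5.2 corrects for it.

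The documents do not show that the result is biased. The 0 to 4.5 point range for complications rests wholly on the assumed conversion and excess-risk values, and only the 73 per group comes from the plan. An advantage to the test group is the likelier direction, but lost PN conversions could offset or reverse it. A conversion rule in Figure 2 would reduce or remove the point. Confidence is medium. The comparison with PN is listed under the secondary objectives, so the point should not be read as undermining a declared primary comparison.

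**What to change.** In Section 5.1, state that:

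- The between-group comparison in Section 5.4 classifies patients by the technique attempted according to the operative record: the planned approach where recorded, otherwise the technique in use when tumour dissection began.
- Attempted zero-ischaemia enucleations later clamped or finished as resection stay in the test group.
- The same comparison by completed operation is reported alongside.
- The number of conversions is reported for each group, with the number of records that do not show what was attempted. For those records the completed operation is used, and the report says so. This fallback keeps the original problem in those records, which is why their number matters.
- Conversions to nephrectomy are handled alike in both groups: counted where the records identify them, otherwise named as a limitation.

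Add technique attempted, clamping (yes/no, minutes) and conversion to the perioperative items in Section 5.1. As a clarification, use one control wording, PN with hilar clamping as in Sections 2 and 5.4, in Sections 4.1 and 5.1.

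The cost is some extra extraction from operative records that the study already has to consult. A systematic search of nephrectomy records would cost more and is not required here. Some records will not show the attempted technique, and the result for the new technique may be less favourable. If conversions prove rare, the counts will show that the point is minor.

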### **6.3 Statistics**

Data entry: Enter the age, gender, kidney cancer stage and prognosis follow-up of the subjects.

Data management: The data are presented by number, and all personnel except the initial data entry personnel do not have access to the subjects' initial information (including subjects' personal information such as subjects' names, addresses, occupations and other sensitive information). There is no direct contact between the data entry personnel and the subjects, and all privacy of the subjects is protected from disclosure.

All hypothesis tests are two-sided, and differences are considered statistically significant at  $P < 0.05$ . Baseline data are evaluated for comparability between groups, and two-tailed statistical tests are performed at the  $\alpha=5\%$  level. The chi-square test or Fisher's exact probability method is used for comparison between groups for count data, the t-test for comparison between groups for measurement data, and the rank sum test for comparison between groups for nonparametric variables.

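### Hypertension, type 2 diabetes and antithrombotic use are not named for description, balancing or adjustment, and follow-up GFR and bleeding are compared unadjusted

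*Combined protocol and SAP*

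**What the plan says.** - **Variables described.** Section 5.1 lists "preoperative conditions (age, sex, Anatomy of tumor, RENAL score, ABC score, preoperative renal function". It names no comorbidity and no medication.
- **Variables balanced.** Section 5.2 corrects and screens the groups until there is "no statistical difference in the number of patients, gender age, tumor anatomy, renal function and other preoperative conditions between the two groups". The criterion is p > 0.05 by "t-test/rank sum test".
- **Exclusions.** Section 4.2 item 1 removes patients with "serious cardiac, hepatic, renal and hematopoietic diseases; and other physical conditions that make them unsuitable for the test in question", as judged by the investigator. Item 4 names "type I diabetes, psoriasis or vitiligo requiring systemic treatment, etc", so type I is the only diabetes mentioned. Item 6 removes other kidney diseases, including stones and glomerulonephritis.
- **Data entry.** Section 6.3 says: "Enter the age, gender, kidney cancer stage and prognosis follow-up of the subjects".
- **Analysis.** Section 5.4 compares margins, postoperative and follow-up renal function, survival rate, complications and bleeding by t-test or rank sum test and one-way regression. It adds a multifactorial Cox regression for survival. Section 3 also mentions multi-factor regression. Neither section lists covariates.
- **Design.** Section 3 describes a retrospective study of 73 zero-ischemia enucleations and 73 conventional partial nephrectomies from 2014 to 2022.

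**The concern.** Without randomisation, the comparison depends on which baseline factors are recorded, balanced and adjusted for. Three ordinary ones are unnamed. On general clinical grounds, which the documents do not state, hypertension and type 2 diabetes affect renal function over years and survival, and antithrombotic drugs affect bleeding.

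The outcomes exposed are central ones. Change in GFR and overall survival are in the main objective (section 2), intraoperative blood loss is a named safety measure there, and section 3 adds intermediate and long-term renal function. Balancing preoperative renal function equalises the starting level of GFR but need not equalise its later decline. Nothing on the balancing list stands in for antithrombotic use. If the groups differ on these factors, part of that difference would be read as an effect of the operation. If the fields are never abstracted, no later analysis can adjust for them.

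**Working it through.** **1. Where each factor appears**

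| Place | Hypertension | Type 2 diabetes | Antiplatelet/anticoagulant |
|---|---|---|---|
| 4.2 Exclusions | not named | not named (type I only) | not named |
| 5.1 Description | not named | not named | not named |
| 5.2 Balancing | not named (open-ended phrase) | not named (open-ended phrase) | not named (open-ended phrase) |
| 3 and 5.4 Models | covariates unlisted | covariates unlisted | covariates unlisted |
| 6.3 Data entry | not named | not named | not named |

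**2. What the balance rule would accept**

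Suppose the factors were added under the open-ended phrase in 5.2. From the plan: 73 per group, and balance accepted at p > 0.05. For a yes/no factor, section 6.3 calls for a chi-square or Fisher test. The counts are chosen for illustration.

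Take 18/73 (24.7%) versus 29/73 (39.7%):
- difference = 11/73 = 0.1507
- pooled proportion = 47/146 = 0.3219
- standard error = √(0.3219 × 0.6781 × 2/73) = 0.0773
- z = 0.1507/0.0773 = 1.949; uncorrected chi-square = 3.80; p = 0.051

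The rule accepts this gap of about 15 points. One more patient, 18 versus 30, gives p = 0.034 and fails. Fisher's exact test is more lenient: 18 versus 29 gives p = 0.076, and 18 versus 30 gives 0.052. Other accepted pairs by uncorrected chi-square are 15/73 versus 25/73 (20.5% versus 34.2%, p = 0.064) and 22/73 versus 33/73 (30.1% versus 45.2%, p = 0.060).

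Power to detect a true 10-point imbalance with 73 per group, two-sided 0.05, at assumed prevalences:

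| Prevalences | Power |
|---|---|
| 10% vs 20% | 39% |
| 20% vs 30% | 28% |
| 30% vs 40% | 24% |
| 40% vs 50% | 23% |

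An imbalance of roughly 18 to 23 points is needed for 80% power.

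**3. What an imbalance could do (assumed inputs throughout)**

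One group is set at 40% prevalence and the other at 25%, 30% or 35%. The factor multiplies the hazard of death by h = 2 or 3, or adds 4 to 10 points of GFR loss. It is left out of the analysis, and the operation has no effect.

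- Approximate apparent hazard ratio = (1 + p_low(h − 1)) / (1 + 0.40(h − 1)), for the lower-prevalence group against the other
- GFR bias = gap × added loss

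| Gap | HR, h = 2 | HR, h = 3 | GFR bias, points |
|---|---|---|---|
| 15 points | 1.25/1.40 = 0.89 | 1.50/1.80 = 0.83 | 0.6 to 1.5 |
| 10 points | 1.30/1.40 = 0.93 | 1.60/1.80 = 0.89 | 0.4 to 1.0 |
| 5 points | 1.35/1.40 = 0.96 | 1.70/1.80 = 0.94 | 0.2 to 0.5 |

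If the other group carries the excess, the ratios invert: 1.40/1.25 = 1.12 and 1.80/1.50 = 1.20 for the 15-point gap. That gap is close to the largest the rule accepts, so the first row is near the upper end. The calculation gives no credit for balancing on age and renal function, which would absorb part of the effect.

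**The case against.** The strongest reply is that the plan is less closed than it looks.

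- **Open-ended wording.** The phrase "gender age, tumor anatomy, renal function and other preoperative conditions between the two groups" could include these factors. Section 5.1 says what is described and need not be the full collection form. The lists are plainly incomplete: the data-entry line in 6.3 omits GFR, bleeding and tumour scores, all of which are analysed. Figure 2 is not shown. This stands. The accurate statement is that the factors are not named, so their control is not assured; it would be wrong to say that they cannot be covered.
- **Exclusions.** Items 1 and 6 bear directly on GFR, bleeding and survival and remove the most severe comorbidity. This also stands and narrows the point. Ordinary hypertension, type 2 diabetes and antithrombotic use need not exclude anyone.
- **Planned multivariable models.** The Cox covariates are unlisted, so it is not established that comorbidity would be left out of the survival model. This stands for survival. It does not answer the one-way comparisons of follow-up renal function and bleeding that 5.4 specifies.
- **Direction.** A reader might infer that surgeons clamp patients at high bleeding risk, so that antithrombotic users collect in the control group and off-clamp surgery looks safer. The documents do not support this. They do not say how clamping was chosen or who took these drugs. Section 1 reports nearly 100 zero-ischemia cases in the last 3 years, against an inclusion window of 2014 to 2022, so calendar period may explain much of who received which operation.

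**Conclusion.** The point holds as a gap in named confounders combined with a stated unadjusted analysis. Following the plan as written leaves follow-up GFR and bleeding open to confounding by milder comorbidity and medication, and leaves overall survival open unless the Cox covariates happen to include them. The p > 0.05 screen is not a safeguard, because it accepts gaps of about 14 to 15 percentage points in the examples worked by uncorrected chi-square.

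Neither the direction nor the size of any bias can be derived from the documents. The hazard ratios and GFR figures above rest on assumed prevalences and effects and show only what is possible. The conclusion assumes that the three factors affect these outcomes, which is general clinical reasoning, and that no variable list in the missing figure already names them. The change should be made, though the practical importance of the gap remains uncertain.

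**What to change.** 1. Abstract hypertension, type 2 diabetes and antiplatelet or anticoagulant use at admission from the existing records. Add them to the lists in 5.1 and 5.2.
2. Report the between-group difference in each, preferably as a standardised difference, and do not rely on p > 0.05 as evidence of balance.
3. In 5.4, replace the one-way comparison of follow-up GFR with a regression adjusted for hypertension, diabetes and baseline GFR.
4. Adjust the intraoperative bleeding comparison for antithrombotic use.
5. Name hypertension and diabetes as covariates in the overall-survival Cox model, or use one comorbidity score if deaths are few.
6. State how missing comorbidity and medication fields will be handled.

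The cost is slightly more abstraction, some missing fields in older records (the window opens in 2014) and a few degrees of freedom. No patient contact is needed and clinical care does not change.

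### Operating surgeon, surgical approach and year of surgery are not named as baseline, balancing or model variables, and most group comparisons are unadjusted, so surgeon or era effects can be read as procedure effects

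*Combined protocol and SAP*

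**What the plan says.** Section 5.1 divides patients by the operation they had. Zero-ischemic enucleation is the test group and partial nephrectomy (PN) the control. Its preoperative description covers "age, sex, Anatomy of tumor, RENAL score, ABC score, preoperative renal function".

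Section 5.2 then corrects and screens the groups until tests show no significant difference in "gender age, tumor anatomy, renal function and other preoperative conditions between the two groups".

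Section 5.4 takes the procedure as the exposure. For margins, renal function, complications and bleeding it states: "T-test/rank sum test and one-way regression are used to compare the efficacy indexes". Section 6.3 adds chi-square or Fisher tests for counts. None of these is adjusted. The one multivariable between-group analysis in 5.4 concerns "survival outcomes between the two groups by multifactorial cox regression", and its covariates are not named. Section 3 is general: "T-test, rank sum test, multi-factor regression, and cox regression are used to investigate the effects of each factor". It gives no covariate list either.

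On the operators, the Research Background says "enucleation requires surgeons to have a better understanding of the anatomical relationship around the tumor" and that "its surgical difficulty is higher than that of traditional PN". It adds that PN is what the majority of surgeons do. On timing it says: "In the last 3 years, our team has performed nearly 100 cases of zero-ischemic renal tumor enucleation". Sections 3 and 4.1 admit surgery from 2014 to 2022.

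**The concern.** In a non-randomised comparison, whatever decided which operation a patient received is a candidate confounder. Here that includes who operated, by what route and when. The protocol itself makes this plausible, since it describes enucleation as more demanding and places a large zero-ischemia series in recent years.

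Operation time, blood loss, complications, margins and renal function can all depend on the operator and on current practice. If surgeon or era differs between the groups, an unadjusted comparison credits that difference to the procedure. Screening the listed patient and tumour factors until p > 0.05 does not remove imbalance in a factor that nobody recorded.

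The secondary objective in Section 2, the difference between the two operations, depends on this comparison.

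**Working it through.** **1. Where each variable appears**

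| Place | Named | Surgeon, approach or year named? |
|---|---|---|
| 4.1, 4.2 eligibility | age, stage, 2014–2022 window, comorbidity, anatomy | window only, as an entry limit |
| 5.1 description | six preoperative factors | no |
| 5.2 balancing | gender, age, anatomy, renal function, plus an open-ended remainder | no |
| 5.4 margins, renal function, complications, bleeding | procedure only | no |
| 5.4 survival (Cox) | covariates unspecified | no |
| 3 regression | covariates unspecified | no |

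**2. Timing.** Counting 3 years back from the protocol date (February 2023) gives about early 2020. If the 73 test cases come mainly from that series, they cluster in roughly the last three of nine calendar years, while controls may come from any of the nine. The text does not say that no zero-ischemia case was done before then, so this is a likely imbalance and not a proven one.

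**3. The plan's own figure.** The sample size of 73 per group (146 in total) cannot be reproduced, because Section 3 gives no value for p0, p1 or power. At two-sided 5% and 80% power, without continuity correction, several pairs lead to about 73 (for example p0 = 0.10 with p1 about 0.28, or p0 = 0.20 with p1 about 0.41). The point does not rest on this figure. Only n = 73 and two-sided α = 0.05 are carried forward.

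**4. Possible bias, binary outcome.** All rates and imbalances are assumed, and there is no true procedure effect. The complication rate is 10% in a favourable surgeon or approach stratum and b in the other. A share f of each group lies in the favourable stratum.

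- Group rate: p = 0.10f + b(1 − f).
- P(reject) ≈ Φ{[|p1 − p0|√73 − 1.96√(2p̄q̄)] / √(p1q1 + p0q0)}.

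| f in the two groups | b | Group rates | Spurious difference | False positives |
|---|---|---|---|---|
| 50% / 50% | 20–30% | equal | 0 | 5% |
| 90% / 30% | 20% | 11% / 17% | 6 points | 18% |
| 90% / 30% | 30% | 12% / 24% | 12 points | 47% |
| 100% / 0% | 20% | 10% / 20% | 10 points | 39% |
| 100% / 0% | 30% | 10% / 30% | 20 points | 86% |

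Either group could be the favoured one.

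**5. Possible bias, continuous outcome (such as GFR change).** Bias in SD units = stratum effect × imbalance, and SE = √(2/73) = 0.165. With a 60-point imbalance:

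- effect 0.3 SD: bias 0.18 SD, false positives 19%;
- effect 0.5 SD: bias 0.30 SD, false positives 44%.

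**6. Clustering, a separate matter from confounding.** Assume 3 surgeons per group, none operating in both, and an intraclass correlation (ICC) of 0.02, 0.05 or 0.10. The design effect 1 + (73/3 − 1) × ICC is 1.47, 2.17 or 3.33. The true error of a nominal 5% test, 2{1 − Φ(1.96/√DE)}, is then about 11%, 18% or 28%. Surgeon numbers, overlap and ICC are all invented for this illustration.

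**The case against.** The strongest reply is that the text shows an unspecified covariate set and not a wrong one. The 5.1 list is descriptive, 5.2 ends with an open category, and neither Section 3 nor the Cox model restricts its covariates. This stands in part. A reader might infer that the plan adjusts for patient and tumour factors only, and the documents do not support that. But the open wording names neither surgeon nor approach, a surgeon is not naturally a patient's preoperative condition, and the 5.4 comparisons of margins, renal function, complications and bleeding are unadjusted however that wording is read.

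Second, imbalance is inferred. The remarks on difficulty and on usual practice concern surgeons in general, one team is described, and the same surgeons may have done both operations. Approach is never mentioned and may not vary. Figure 2 is not shown. All of this stands, and it is why the conclusion is conditional.

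Third, a reader might infer that the bias favours enucleation because its surgeons are more skilled. The documents do not support a direction. A harder operation early in a team's experience could look worse than it is. Difficulty intrinsic to the operation is also part of its effect and not a confounder.

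Fourth, adjusting for surgeon has limits. If no surgeon did both operations, a surgeon fixed effect or stratum leaves the procedure effect inestimable. Survival events may also be few, since the Background reports no local recurrence in more than 500 enucleations. Both limits stand and shape the fix.

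**Conclusion.** The point holds in conditional form. The plan names no surgeon, approach or year variable, and it compares most outcomes without adjustment, so following it as written leaves any imbalance in these factors in the result. The protocol's own Background makes such imbalance plausible for surgeon and era. Whether it exists, how large it is and which way it acts cannot be known from the documents. If the factors are balanced, there is no bias.

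The figures of 6 to 12 points and 18% to 47% false positives show what moderate assumptions would produce, and are not estimates for this study. The clustering error rates of 11%, 18% and 28% should not be read as the study's true error. They rest wholly on assumed surgeon numbers and ICC, and they measure variance inflation and not confounding.

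This is worth correcting before analysis, because the comparison between procedures cannot be interpreted without knowing who operated in each group, how and when.

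**What to change.** 1. **Section 5.1:** add operating surgeon, approach (open, laparoscopic, robotic) and year of surgery to the variables, and tabulate them by group.
2. **Section 5.4, non-survival outcomes:** add adjusted regression models for renal function, blood loss and complications, and for margins if events allow. Include the listed baseline factors plus surgeon, approach and year where the groups overlap. These must be written in as new models, because the only multivariable model now in 5.4 is for survival.
3. **Section 5.4, survival:** stratify the Cox model by surgeon and avoid adding many terms. Strata with only one procedure contribute nothing to the comparison, so report how many patients and events lie in strata with both.
4. **Sensitivity analysis:** restrict the comparison to surgeons who did both operations.
5. **If surgeon and procedure do not overlap:** do not fit surgeon effects, and state that the comparison cannot separate surgeon from procedure.

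Cost: a few extra data fields and some SAP wording. Year must already be checked to apply the 2014–2022 criterion. The documents name no source for surgeon and approach, so it is an assumption that the surgical records hold them. The statistical price is a wider confidence interval, possibly much wider if few surgeons or years contain both operations.
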